6.7.4 Informed consent

All participants will provide written informed consent at the screening visit. The Informed Consent Form will be signed and dated by the participant before he or she enters the trial. The nurse will explain the details of the trial and provide a further copy of the PIS, ensuring that the participant has had sufficient time to consider participating or not. The nurse will answer any questions that the participant has concerning study participation.

Informed consent will be collected from each participant before he or she undergoes any interventions (including physical examination and history taking) related to the study. One copy of this will be kept by the participant and one will be kept by the Investigator at site. In addition, a copy of the signed consent form will be sent securely to Keele Clinical Trials Unit (CTU), separately to any study data or case report forms. The consent forms will be stored in a secure location at Keele CTU in a different location to study data.

Should there be any subsequent amendment to the final protocol that might affect a participant's participation in the trial, continuing consent will be obtained using an amended consent form, which will be signed by the participant.

7. TRIAL STUDY TREATMENT AND REGIMEN

7.1 Treatment in intervention arm:

Allopurinol-based treat-to-target ULT is the healthcare technology being assessed. It will be delivered by practice nurses trained in delivering and managing a protocol driven allopurinol-based treat-to-target regimen.

The steps of the treat-to-target ULT protocol are consistent with national and international recommendations and recent studies [12–14, 34–35]. These are:

 Allopurinol commenced at a dose of 100 mg/day at the baseline visit in the experimental arm. Participants already on sub-therapeutic dose of allopurinol will have its dose increased by 100 mg/day. Individualized education about gout and principles of management including treat-to-target-ULT discussed. Lifestyle riskfactors of gout discussed. Advice for improving them provided as adjuncts to treatto-target-ULT. Arthritis Research UK (recently renamed Versus Arthritis) leaflet on

> Page 37 of 71 Treat to target in gout Protocol Final Version 1.1 date 29 May 2019

gout provided.

- Participants of Han Chinese, Thai or Korean ethnicities will be commenced on Febuxostat 80 mg/day as first line ULT, as they are at a high risk of developing DRESS syndrome from Allopurinol treatment.
- A booklet containing study contact details, and a table for recording current ULT dose, serum urate level, date of next serum urate blood test, and date of next repeat ULT or flare prophylaxis prescription will be provided to participants in the intervention arm.
- Serum urate measured after 4 weeks, as serum urate is a negative acute phase reactant [13] and the urate level commonly reduces during a flare. If a participant is experiencing gout flare at this time, the visit will be postponed till 2 weeks after the flare has resolved completely. This is a treatment visit and will be conducted by general practice nurses, phlebotomists or other suitably trained staff.
- Allopurinol dose increased by 100mg/day if the serum urate is ≥360 µmol/L at week 4.
- Process repeated approximately 4-weekly until serum urate is <360 µmol/L, or maximum licensed or tolerated dose of allopurinol reached.
- Allopurinol discontinued if unable to achieve serum urate <360 µmol/L due to side effects or intolerance of high doses, or failure to do so despite maximum licensed dose, and febuxostat 80 mg/day started as per the NICE Technology Appraisal 164.
- The dose of febuxostat increased 4 weeks later to 120 mg/day if the serum urate ≥360 µmol/L.
- If serum urate is ≥360 µmol/L despite maximum licensed dose of allopurinol or febuxostat, uricosuric drugs, e.g. sulfinpyrazone co-prescribed, with 4-weekly serum urate measurement and dose up-titration.
- Monotherapy with uricosuric drugs such as sulfinpyrazone will be utilized if both allopurinol and febuxostat are contraindicated or not-tolerated.
- Once the treatment target is reached (i.e. serum urate < 360 µmol/L), the practice-staff will confirm with the participant that this was at least two weeks clear of the previous gout flare. For participants experiencing a gout flare in this period, the serum urate will be measured at least 2 weeks from the date of self-reported resolution of the gout flare. If the serum urate is ≥360 µmol/L at this point, the dose of ULT will be increased as outlined above.
- Once serum urate is <360µmol/L, ULT prescription will occur 2-monthly without any face-to-face visits. Four-weekly serum urate measurements will stop once the serum urate level is <360µmol/L.
- Participants will have serum urate measured at year 1 and year 2 research assessment visits (see later page 42). The practice-staff of participants randomized to the intervention arm will be made aware of the results of these tests. They will inform the study participants, and those no longer achieving treatment target will be reviewed to discuss adherence with ULT. Participants adherent to ULT will have the dose of ULT increased where possible using treat to target strategy outlined above.
- Participants can request further clinical visits, or telephone advice from the practice nurse, for their gout, as needed.
- The lead applicant, and two of the clinical co-investigators (ER, MS with CDM and PL deputizing in case of leave) will advise the practice nurse and the GP signing the prescription if required.

[figure not shown]
Page 38 of 71 Treat to target in gout Protocol Final Version 1.1 date 29 May 2019

• Each participating GP surgery will have a nominated GP for signing the ULT prescription, and the research trained practice nurses will not treat control arm gout patients for the study duration. The practice nurse will be required to not disseminate their experience with ULT to other staff members during the study.

Prophylaxis: As the initiation of ULT can increase the risk of gout flare occurrence, prophylaxis to prevent gout flares will be prescribed for six months as part of the treat-to-target ULT regimen, as recommended in national and international gout treatment guidelines [12–14].

- Colchicine (0.5 mg twice a day) will be used first line for this purpose. The dose of colchicine will be halved if the study participant is on any medication for which this is recommended by the British National Formulary (See Appendix 1), or is aged over 70 years, or has renal impairment. Additionally, if colchicine is not tolerated due to side effects such as diarrhoea, its dose will be halved. If half-dose colchicine is not tolerated, it will be discontinued. Colchicine will not be prescribed if there are contraindications to its use as per the BNF (See Appendix 2).
- Naproxen (250 mg twice a day) along with a generic proton pump inhibitor (e.g. omeprazole 20 mg/day if not already prescribed) will be used second-line if there are contraindications to colchicine prescription or it is not tolerated. Low-dose NSAIDs will not be prescribed in the presence of contra-indications specified in the BNF and NICE clinical knowledge summary for NSAIDs (See Appendix 2).
- Participants unable to tolerate either of the two prophylactic medicines will continue on ULT without prophylaxis, but will be provided with rescue packs of oral prednisolone (30 mg/day for 1 week) to treat gout flares should they occur.

[figure not shown]
Page 39 of 71 Treat to target in gout Protocol Final Version 1.1 date 29 May 2019

Page 40 of 71 Treat to target in gout Protocol Final Version 1.1 date 29 May 2019

Figure 2 Flare prophylaxis

¹Contraindications to colchicine as per BNF. ²Colchicine dose reduction criteria: either of interacting medicines (See appendix 1), or age > 70 years, or eGFR 30-50 ml/min.

Treatment of flares of gout: Participants in both arms of the study will be able to get treatment for flares of gout from their GP as before they entered the study.

7.2 Treatment in control arm:

Page 41 of 71 Treat to target in gout Protocol Final Version 1.1 date 29 May 2019

Study participants will be able to consult their GP as usual and receive treatment for flares of gout and ULT according to the GP's usual practice and their symptoms. Participants in the control arm will attend at the screening, baseline, year 1 and year 2 research assessment visits.

7.3 Concomitant treatments:

All concomitant treatments will be allowed in the control arm. Participants in the intervention arm will be commenced on treat-to-target urate lowering treatment, and flare prophylaxis. They will also be allowed to continue on, or, commence any other concomitant treatment as necessary. They will not have access to a structured allopurinol based nurse-led treat-to-target ULT. Our own clinical experience and published research suggests that such treat-to-target-ULT is very uncommonly prescribed by GPs in the UK, with the vast majority of gout patients not being prescribed any ULT, or being prescribed sub-therapeutic fixed doses of ULT e.g. allopurinol 300 mg/day [2].

7.4 Internal pilot:

Ninety participants in the East and West Midlands will be recruited into the internal pilot, randomized to active or control arm, receive study interventions to be used in the randomized controlled trial as detailed above, and be followed up until year 1 research assessment. Participants in the internal pilot will continue on ULT while progression to the main trial is confirmed. The criteria for progression to the main trial are described in the statistics section. Data from baseline to year 1 research assessment will be used to assess feasibility outcomes, and gain a preliminary estimate of treatment efficacy.

7.6 Data collected at research assessments

The research nurse in each region will collect data from study participants at the baseline, year 1 and year 2 research assessment visits.

	Research assessment				
	Screening	Baseline	Year 1	Year 2	
Sex	Х				
Date of birth	Х				
Serum urate	Х		Х	Х	
Serum creatinine	Х		Х	Х	
Inclusion criteria	Х				
Exclusion criteria	Х	Х			
Prescription drugs		Х	Х	Х	
Comorbidities		Х	Х	Х	
Body mass index		Х	Х	Х	
Blood Pressure		Х	Х	Х	
Tophus count		Х	Х	Х	
Tophus size		Х	Х	Х	
Urine collection		Х	Х	Х	
Side-effects to ULT			Х	Х	
GIS ¹		Х	Х	Х	
EQ-5D-5L		Х	Х	Х	
TSQ ²			Х	Х	
MMAS-8 ³			Х	Х	
Pill count		Х	Х	Х	
Gout flare and					
Healthcare use diary		Given	Collected	Collected	

Table 11: Research assessments

¹Gout impact scale, ²Treatment satisfaction questionnaire, ³Morisky Medication Adherence Scale-8.

If a study participant brings any medication to the year 1 and year 2 research assessments that are in excess of their requirements and need disposing off, the research staff, after completing the pill count, will advise them to return the excess medications to their local NHS pharmacy from which it was dispensed.

Page 44 of 71 Treat to target in gout Protocol Final Version 1.1 date 29 May 2019

7.7 Data collected from GP surgery:

Data about serum urate, current ULT and flare prophylaxis treatment (name and dose), any temporary treatment discontinuations and reasons, side-effects, and recommended treatment if applicable (name and dose) will be collected by general practice staff at each dose increase visit in the intervention arm as part of usual medical care.

Data about the following variables will be collected from GP surgery records at year 1 and year 2 research assessment visits, along with their dates. This will be collected by GP surgery staff or the local research staff depending on local preference at the GP surgery.

Serum urate (results, dates)

ULT prescriptions (name, daily dose, duration, dates of prescription)

Flare prophylaxis prescriptions (name, daily dose, duration, dates of prescription)

GP surgery consultations for flares (dates)

GP telephone consultations for flares (number, dates)

Out-of-hours emergency GP surgery attendance for flares (dates)

Flare treatments (name, daily dose, total quantity, dates of prescription)

Referral to hospital outpatient clinic for gout (dates of referral)

Hospitalization for gout flare (number, admission and discharge dates)

A&E attendance for gout flare (number, admission and discharge dates)

Side-effects to ULT (specify event, dates)

Side-effects to flare prophylaxis (specify events, dates)

Side-effects to flare treatment (specify events, dates)

7.8 Data collected by study participants:

Electronic acute gout flare diary: A mobile phone text-messaging system will be used to collect data on occurrence and severity of gout flares.

Text message system:

- Participants will receive a welcome text message at the baseline visit after randomisation to confirm their telephone number, welcome them to the study and advise them that they will receive SMS messages going forward.
- Study participants will initiate the text-messaging service by texting the word "gout" when they experience a flare. If they forget to text on the first day, they can still text "gout" at a later date.
- The messaging system will send short text messages enquiring about pain severity (0–10 numerical rating scale), presence of warm joint, and swollen joint [47]. This will be used to classify self-reported gout flares as meeting the criteria for a flare of gout [47]. For a flare to be present, the episode should meet the flare definition criteria, i.e. at least 3 of the following four: pain severity >3/10, presence of warm

Page 45 of 71 Treat to target in gout Protocol Final Version 1.1 date 29 May 2019

joint, swollen joint, and self-reported flare [47]. A single reminder will be sent for non-response.

- On day 1 of self-reported gout flare the messaging system will ask participants how long they have had the flare for, and send a message asking participants to complete EQ-5D-5L in the paper diary within next 48 hours.
- The messaging system will then send daily text messages enquiring about pain severity on a 0–10 numerical rating scale (NRS) each morning for up to 7 days, with a reminder to answer the question if needed. This suite of messages will be discontinued if the participants responds with a score of 0 or 1 on 2 consecutive days. The pain numerical rating scale is endorsed by Outcome Measures in Rheumatology Clinical Trials for measuring the severity of flares of gout [48].
- After 7 days, or if there are two days with NRS 0 or 1, the participant will receive a thank-you text, and, a reminder to complete the questions regarding wellbeing during gout flare and gout concern during flare domains of GIS, healthcare utilization during gout flare and date the gout flare resolved in a paper diary.
- To mitigate the risk of a single flare being counted as multiple flares, a flare will be defined as an incident flare if there is at least a 48-hour time period between the end of the previous flare reporting period and the start of next flare. If the interval between is smaller than 48 hours, they will be regarded as a single episode. Flares with no reported daily pain NRS will be excluded from analysis of secondary outcomes e.g. flare severity and duration.
- If the participant forgets to text when the flare is occurring, he or she will be able to contact the research team by phone during weekday office hours to report the date of onset and end of the most recent gout flare. The researcher will elicit information about pain severity (0–10 NRS), presence of warm joint, swollen joint, to classify self-reported gout flares as meeting the criteria for gout flare [47]. Daily pain severity and EQ-5D-5L will not be available for such episodes.

Paper diary: A paper diary will be available for those who do not have a mobile phone or do not wish to use text-messages.

Reminders: As study participants can forget completing the gout flare diary, they will receive a text or a letter (if they do not have a mobile phone), every 2 months, reminding them to complete the gout flare diary, and, if they had a flare for which they did not complete the flare diary, they will be encouraged to phone dedicated research staff in the research team to provide these data.

Health related QoL during gout flares: To account for QoL during gout flares, the participants will complete the EQ-5D-5L once within the first 48 hours of onset of each gout flare. The collection of EQ-5D-5L also allows us to bring health status during gout flare into overall cost-utility analysis.

The wellbeing during gout flare and gout concern during flare sub-scales of the GI S, which captures disease specific QoL during the most-recent gout flare, will be completed within 2 days of complete resolution of the acute gout flares.

Loss of productivity during gout flares: Information about the number of days on which gainful paid employment was lost during each flare will be recorded in the gout flare diary.

Healthcare utilisation for gout during flares: Medicines taken for gout flare, GP visits, A&E visits, out of hours-GP visits, home GP visits, hospitalization, number of days hospitalized.

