[2] If target serum urate is not achieved in <50 participants by year 1, and <60% are adherent to ULT at year 1, it suggests such low concordance with the intervention that a meaningful effect on the rate of flare occurrence is unlikely, and proceeding with this trial would be futile.

[3] The sample size allows for up to 20% loss to follow-up. A high attrition rate of 21–30% in the pilot study likely indicates poor tolerability of the study processes, and we will explore and address the reasons for this. An attrition rate >30% will affect the validity of the findings, making proceeding with the study futile.

[4] If information in the electronic flare diary is 70–84% complete on any outcome measure (e.g. pain severity, flare stop date) we will address any problems. If the flare diary is completed in <70% instances for the primary outcome, this will not be a feasible method for collecting outcome data and other methods of collecting flare data, e.g. paper diary or phone calls, will be used.

Choice of method of outcome measure collection based on internal pilot: If the data quality (missingness) is substantially better in the paper diary, we will abandon the SMS system for collecting primary outcome data. Similarly, we will abandon the SMS for

Page 49 of 71 Treat to target in gout Protocol Final Version 1.1 date 29 May 2019

collecting primary outcome data if a substantial number of people phone in during/after their gout flare to provide data on primary outcome, and do not use real-time SMS.

Completeness of the flare diary in internal pilot

Participants can phone the CTU if they forget to send in text messages when they are experiencing a flare (see above). Apart from this, they will be sent text message reminders at 2 monthly intervals and requested to phone and inform the research team if there were any gout flares they did not report at all. This will be used to assess the completeness of the text message system in collecting data on the primary outcome (number of acute gout flares). Where a flare diary is initiated, we will measure the proportion of completed responses for each outcome of interest, i.e. erythema, pain severity, swelling and tenderness on day 1, EQ-5D-5L on day 2, daily pain score.

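### Section 7.8 times the in-flare EQ-5D-5L from the participant's text but defines it from flare onset, and can send the GIS and end-date reminder before a long flare has resolved

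*Protocol*

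**What the plan says.** All of this is in the Protocol; no SAP is at hand.

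**EQ-5D-5L during a flare.** Under the text message system in section 7.8, the participant starts the message series by texting. Lateness is allowed, with no upper limit: "If they forget to text on the first day, they can still text" afterwards. On the first day of the series the system asks how long the flare has already lasted and will "send a message asking participants to complete EQ-5D-5L in the paper diary within next 48 hours". The paragraph on quality of life during flares in the same section sets a different clock: "the participants will complete the EQ-5D-5L once within the first 48 hours of onset of each gout flare". Section 8.2 (completeness of the flare diary) lists "EQ-5D-5L on day 2, daily pain score". Section 8.4 asks only for one EQ-5D-5L in each flare.

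**GIS flare domains and resolution date.** Daily pain texts run for up to 7 days and stop earlier after two consecutive scores of 0 or 1. Then: "After 7 days, or if there are two days with NRS 0 or 1, the participant will receive a thank-you text", with a reminder to fill in the GIS flare domains, healthcare use and the resolution date in the paper diary. The GIS flare domains, however, "will be completed within 2 days of complete resolution of the acute gout flares". A general text or letter every 2 months also reminds participants about the diary.

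**Use.** Table 12 lists in-flare EQ-5D-5L, GIS and flare duration as secondary endpoints. Section 8.4 puts the in-flare EQ-5D-5L, together with flare duration, into the QALY.

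**The concern.** For each of these two measures, section 7.8 states when it should be taken and also sets a prompt that can fall at another time.

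For the EQ-5D-5L, the prompt follows the text while the definition follows onset. A participant who texts late and does as the message asks produces a form that the definition excludes. Nothing says whether such a form counts. Flares reported by phone are covered, because EQ-5D-5L is declared unavailable for them; late-texted flares are not covered.

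For the GIS, a flare still active when the texts end gets its reminder before there is any resolution to report. The participant may then complete the GIS during the flare, leave the resolution date blank, or enter it prematurely.

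What is at stake is whether the in-flare EQ-5D-5L and GIS mean the same thing from flare to flare, and how complete flare duration is. These are rules of data collection: a form filled in at the wrong time cannot be re-timed at analysis.

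**Working it through.** The protocol states no figure to reproduce, and it gives no distribution of texting delay or flare length. The check is arithmetic on the stated windows, with illustrative delays and durations.

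**1. EQ-5D-5L window**

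Let *d* be the days from onset to the text.
- Prompted window: [d, d + 2] days from onset (48 hours from the message).
- Defined window: [0, 2] days from onset.
- Overlap = max(0, 2 − d); share of the prompted window inside the defined one = overlap / 2.

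| d (days) | Prompted window | Overlap (days) | Share |
|---|---|---|---|
| 0 | 0 to 2 | 2 | 100% |
| 0.5 | 0.5 to 2.5 | 1.5 | 75% |
| 1 | 1 to 3 | 1 | 50% |
| 1.5 | 1.5 to 3.5 | 0.5 | 25% |
| 2 | 2 to 4 | 0 | 0% |
| 3 | 3 to 5 | 0 | 0% |

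From a delay of two days, a participant who waits for the prompt and follows it cannot meet the onset-based definition.

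**2. GIS and resolution-date reminder**

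Let *D* be the day of resolution, counted from onset. The reminder comes at the earlier of two times:
- the cap, day d + 7;
- two consecutive pain scores of 0 or 1, taken here as about day D + 2. This assumes that such scores coincide with resolution.

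So the reminder day is R = min(d + 7, D + 2). The GIS is due in [D, D + 2], so R − D should lie between 0 and 2.

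| D (days) | R − D, d = 0 | R − D, d = 2 |
|---|---|---|
| 3 | 5 − 3 = +2 | 5 − 3 = +2 |
| 5 | 7 − 5 = +2 | 7 − 5 = +2 |
| 7 | 7 − 7 = 0 | 9 − 7 = +2 |
| 8 | 7 − 8 = −1 | 9 − 8 = +1 |
| 10 | 7 − 10 = −3 | 9 − 10 = −1 |
| 14 | 7 − 14 = −7 | 9 − 14 = −5 |

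For short flares the reminder falls inside the GIS window, at or near its edge. Whenever D exceeds d + 7, it precedes resolution. The protocol contemplates flares of that length: Table 8 counts resolution within 14 days among the features of a typical episode. That is an upper bound in a classification item, so it says nothing about how many trial flares pass 7 days. After the early reminder, only the 2-monthly one follows. It may still recover a missing end date, but it cannot be relied on to fall within 2 days of resolution.

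**The case against.** Several points on the other side are fair.

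- **Onset is recoverable.** The first message asks how long the flare has lasted, so late forms can be identified. This stands, but it does not move a late form into the defined window. The protocol also does not say what to do with it.
- **The first day of the series could mean the first day of the flare.** That reading would remove the conflict if everyone texted at once. The protocol allows later texting and asks about elapsed duration, so it cannot be assumed.
- **Day 2 in section 8.2 is not a further conflict.** Correct: it can be read as falling within 48 hours of onset.
- **Completeness is monitored.** In the pilot, if the electronic diary is 70–84% "complete on any outcome measure (e.g. pain severity, flare stop date) we will address any problems". This stands for missing entries. It would not detect a form that is complete but mistimed. That item also treats the stop date as part of the electronic diary, whereas section 7.8 puts it in the paper diary.
- **Participants using only the paper diary** are outside the text series altogether. True.

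A reader might also infer four stronger claims, which the document does not support.

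- *Daily pain is taken at the wrong time.* Section 7.8 defines daily pain only as the text series and ties it to neither onset nor resolution. Missing the first days of a late-texted flare, or those after the cap, limits coverage and contradicts nothing.
- *The flare end date is set by the text series.* The participant enters the date of resolution; only the reminder is timed by the texts.
- *Flare duration is biased and a difference between arms shrinks.* This needs assumed inputs throughout. Take gamma durations (shape 2) with means of 6 and 8 days, and end dates obtained for 95% of flares ended by day 7. A true 2.0-day difference is then observed as 1.9, 1.6 or 1.1 days if end dates are obtained for 75%, 50% or 25% of longer flares. The first is negligible, and the last allows little for the 2-monthly reminders. No passage shows that texting delay differs by arm.
- *Late EQ-5D-5L forms harm the QALY.* Suppose the decrement falls linearly to zero over 7, 10 or 14 days, so that its flare average is 50% of the initial value. A form one day after onset carries 1 − 1/7 = 86%, 1 − 1/10 = 90% or 1 − 1/14 = 93%. A form on day 4, after a text on day 3, carries 1 − 4/7 = 43%, 1 − 4/10 = 60% or 1 − 4/14 = 71%. In this model the late forms lie nearer the average, so it gives no ground for discarding them.

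**Conclusion.** The point holds as an inconsistency in data collection within section 7.8, with a looser third statement in section 8.4. The EQ-5D-5L prompt and its definition separate completely once the text is sent two or more days after onset. The GIS and resolution-date reminder precedes resolution in any flare lasting more than 7 days beyond the day of the text.

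The first result follows from the stated windows alone. The second does too, except that its timing for shorter flares assumes that two pain scores of 0 or 1 mark resolution. How many flares are affected cannot be computed, because the protocol gives neither texting delays nor flare lengths.

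The effect is confined to secondary and economic measures: in-flare EQ-5D-5L, GIS and the completeness of flare duration. It does not touch the primary flare count. Bias between arms in duration or QALYs is not shown. The point merits a modest correction because that correction is cheap and mistimed forms cannot be repaired later.

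**What to change.** 1. Name one time anchor for the in-flare EQ-5D-5L and use it in section 7.8 (both places), section 8.2 and section 8.4.
2. Record the completion date on the EQ-5D-5L form, if the diary (not shown) does not already do so. Use the reply on elapsed flare duration to place each form by day since onset. Keep late forms.
3. If the last daily pain score is above 1 at day 7, continue a short automated text until the participant reports resolution, and send the GIS and end-date reminder then.
4. State whether the flare stop date is an electronic or a paper item, so that the pilot completeness check in section 8.2 matches section 7.8.

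**Cost.** A few extra automated texts in long flares, a setting in the in-house SMS system, a date box and some wording. One precaution: section 7.8 counts a new flare from 48 hours after the end of the previous reporting period. The amendment should therefore say whether the added texts extend that period, so that the primary count is not changed unintentionally.
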